1. STUDY PROTOCOL

1.1 Objectives

The research aims to determine the differences in:

- Decrease in IL-1 β levels between benign paroxysmal positional vertigo (BPPV) patients receiving oral lumbrokinase DLBS1033 therapy and those receiving betahistine therapy.
- Decrease in TNF- α levels between BPPV patients receiving oral lumbrokinase DLBS1033 therapy and those receiving betahistine therapy.
- Decrease in VCAM-1 levels between BPPV patients receiving oral lumbrokinase DLBS1033 therapy and those receiving betahistine therapy.
- Quality of life between BPPV patients receiving oral lumbrokinase DLBS1033 therapy and those receiving betahistine therapy.
- Time to improvement of dizziness symptoms between BPPV patients receiving oral lumbrokinase DLBS1033 therapy and those receiving betahistine therapy.

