1.2 Design and Methods

- Type of research: This study is a clinical trial with a double-blind randomized controlled trial design.
- Place and time of research: The study was conducted at the neurology polyclinic of [name] General Hospital, Surakarta. Data collection began after obtaining ethics committee approval and continued until the required sample size was met, from April to August 2024.
- Research population: The actual research population consists of patients at the neurology polyclinic of [name] General Hospital, Surakarta, who met the inclusion and exclusion criteria.
- Research subjects: Subject selection was carried out using purposive sampling.
 - Inclusion criteria: BPPV patients at the neurology polyclinic of [name] General Hospital, aged 18-65 years, diagnosed by a neurologist or neurology polyclinic resident based on a history of worsening vertigo, nausea, vomiting, and imbalance with head movements, and findings of torsional nystagmus with latency, fatigability, and duration less than 60 seconds on Dix-

Hallpike maneuver; able to speak, read, and write Indonesian; and willing to cooperate as research subjects by signing the informed consent form.

- Exclusion criteria: Pregnant and breastfeeding patients; patients with neurological deficits indicative of central vertigo based on anamnesis and physical examination; patients with a history of ear infection, hearing impairment, tinnitus, and head trauma; patients with thyroid disorders, diabetes mellitus, genu osteoarthritis, history of neoplasm, history of heart disease and hypertension, history of ear/mastoid surgery, and currently experiencing other inflammatory and infectious conditions; patients with cognitive impairment based on attention and memory examination; patients participating in other clinical studies within 30 days before screening.
- Drop-out criteria: Patients who could not complete the entire research procedure; patients who did not follow procedures properly; patients who did not complete the DHI and VSS-SF questionnaires after receiving therapy.

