- Sample size: The minimum sample size was calculated using Sopiyudin's sample size¹ formula with a 95% confidence interval (CI) and 5% confidence limits. Based on a total population of 751 peripheral vertigo patients treated at the neurology polyclinic of [name] in the last year, the calculation resulted in a minimum sample of 40 patients. An additional 10% was added to anticipate dropouts, making the total sample size 44 patients.
- Variable identification:
 - Independent variable: BPPV therapy.
 - Dependent variables: inflammation level, quality of life, time to improvement of dizziness symptoms in BPPV patients.
 - Confounding variables: age, body mass index, gender.
- Operational definition of research variables:
 - BPPV therapy: Administration of oral lumbrokinase (DLBS 1033, 2x490 mg daily) or betahistine (2x12 mg daily) for 14 days to diagnosed BPPV patients.
- Research instruments: Dizziness Handicap Inventory (DHI) and Vertigo Symptom Scale Short Form (VSS-SF) questionnaires, and biomarker examination (IL-1 β , TNF- α , VCAM-1) using Human Quantikine R&D Systems kits on a Thermo Fisher Invitrogen auto-analyzer according to manufacturer specifications.
- Randomization protocol: The study protocol involved a two-block randomization to ensure balanced group assignments. The random sequences for the group allocation were generated by independent personnel of the direct study management and kept in sealed

envelopes. This allocation concealment ensured that neither the investigator team nor the participants knew their assigned treatment. Each package was coded with the subject identification number according to the generated random number and assigned to each eligible subject. These codes remained unrevealed until the study's completion.

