2.2 Specific Statistical Methods

- Normality test: The Kolmogorov-Smirnov test was used to check the normality of the data distribution for all variables. The Kolmogorov-Smirnov test was performed to verify the assumption of normal distribution for all variables, confirming that the data met this critical assumption for the subsequent parametric tests.
- Comparison between groups (day 7 and day 14):
 - Independent T-test: This test was used to determine significant differences between the oral lumbrokinase DLBS1033 group and the betahistine group for:
 - Mean DHI scores,
 - Mean VSS-SF scores,
 - Mean TNF- α levels,
 - Mean IL-1 β levels,
 - Mean VCAM-1 levels.
- Analysis of symptom improvement time (multiple repeated ANOVA):
 - Given the significant statistical differences found with the independent T-test, further analysis regarding the time to symptom improvement in BPPV patients receiving oral lumbrokinase DLBS1033 was performed using multiple repeated ANOVA.
- Post-hoc analysis: Tukey B post-hoc test was used to compare the mean scores/levels between groups.

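### The SAP gives significant t-tests as the reason for the repeated ANOVA, so that analysis cannot count as pre-specified or as independent confirmation of them

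*Combined protocol and SAP*

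**What the plan says.** Section 2.2 first lists t-tests between the arms under "Comparison between groups (day 7 and day 14", for five outcomes: DHI, VSS-SF, TNF-α, IL-1β and VCAM-1. It then turns to symptom improvement time and opens with a finding: "Given the significant statistical differences found with the independent T-test, further analysis" was undertaken, in patients "receiving oral lumbrokinase DLBS1033 was performed using multiple repeated ANOVA". Only the lumbrokinase arm is named there.

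A second result appears under the normality test, which is reported as "confirming that the data met this critical assumption for the subsequent parametric tests". A separate bullet adds that "Tukey B post-hoc test was used to compare the mean scores/levels between groups".

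Two other places bear on the point. Section 1.1 lists as an objective the difference in "Time to improvement of dizziness symptoms between BPPV patients receiving oral lumbrokinase DLBS1033 therapy and those receiving betahistine therapy", which is a between-arm question. Section 1.2 describes data collection as finished: it "continued until the required sample size was met, from April to August 2024".

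No section gives a significance level for the tests, a primary outcome, a testing order, the t-test that opens the way to the ANOVA, or what happens if no t-test is significant.

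**The concern.** An analysis plan should fix what will be run before the arms are compared. Here the stated reason for the repeated ANOVA is that the arms had already been found to differ, and the ANOVA re-uses values from the same patients. If it is then reported beside the t-tests, it looks like a second line of evidence, when part of any agreement follows from how it was selected.

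The one-arm description adds to this. A change over time within the lumbrokinase arm does not answer a between-arm objective, because patients on betahistine may have improved equally. At stake is the standing of the time-course result: whether it can be called planned, and how much it adds to the t-tests.

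**Working it through.** The plan gives no figure on this point, so there is none to reproduce. The check asks how strongly the ANOVA depends on its trigger, and what that does to the error rate.

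**Inputs from the documents.** Visits at day 7 and day 14, and five outcomes (section 2.2). Minimum sample 40, or 44 with the dropout allowance (section 1.2), hence 40/2 = 20 or 44/2 = 22 per arm with equal allocation.

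**Assumptions.** Two-sided 5% tests: the only confidence level given is in the sample-size text ("formula with a 95% confidence interval (CI) and 5% confidence limits"). Normal data, no true arm or time effect, three visits (baseline, day 7, day 14), and equal correlation of 0.3, 0.5 or 0.7 between visits. The trigger is a significant t-test at day 7 or day 14 on the same outcome.

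**Step 1: conditional rates by simulation, 22 per arm.**

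| Correlation | P(trigger) | Arm effect significant, given trigger | Lumbrokinase-only time effect significant, given trigger |
|---|---|---|---|
| 0.3 | 0.094 | 0.314 | 0.135 |
| 0.5 | 0.089 | 0.401 | 0.106 |
| 0.7 | 0.084 | 0.499 | 0.087 |

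Without the trigger, each effect is significant in about 5% of trials. A separate run with 20 per arm gave 0.322, 0.403 and 0.488 for the arm effect, and 0.130, 0.109 and 0.092 for the one-arm time effect. If the model holds only day 7 and day 14, the arm effect given the trigger rises to 0.412, 0.459 and 0.535.

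**Step 2: joint rates.** P(trigger and ANOVA significant) = P(trigger) × P(ANOVA significant given trigger), at 22 per arm:

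- Arm effect: 0.094 × 0.314 = 0.030; 0.089 × 0.401 = 0.036; 0.084 × 0.499 = 0.042. Ungated rate 0.05.
- One-arm time effect: 0.094 × 0.135 = 0.013; 0.089 × 0.106 = 0.009; 0.084 × 0.087 = 0.007. Ungated rate 0.05.
- Arm or arm-by-time effect (conditional rates 0.517, 0.553 and 0.603): 0.049, 0.049 and 0.051. Ungated rate 0.097.

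This must be so: the event that both tests are significant cannot be more probable than the event that the ANOVA is significant.

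**Step 3: how open the gate is.** Five outcomes at two visits make ten t-tests. If any of them could trigger the ANOVA, the chance of at least one false trigger is 1 − 0.95^10 = 0.40 if they were independent, and less if they are correlated. The SAP does not say which t-test counts.

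**Step 4: the one-arm reading.** With 20 lumbrokinase patients and correlation 0.5, a fall of 0.5 SD by day 14 makes the within-arm time effect significant in 47% of runs, and a fall of 1.0 SD in 98%. Neither figure depends on what happens in the betahistine arm.

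**Step 5: the post-hoc test.** With two groups at one visit, a Tukey comparison returns the t-test result. In a numerical check, the t-test, the one-way ANOVA and the Tukey HSD comparison all gave P = 0.1977.

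**The case against.** There is a fair case on the other side, and several parts of it stand.

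- **Error rate.** A reader might infer from the 31–50% that the trial's false-positive rate is inflated. Step 2 shows otherwise: requiring a significant t-test first lowers the joint rate. Had the sequence been fixed in advance, it could be legitimate gatekeeping. What remains is that the SAP shows no such rule.
- **Timing.** A reader might infer that the analysis was chosen after unblinding. The documents do not prove this. The whole text is retrospective, so the past tense cannot separate a data-driven choice from a planned step described later. Time to improvement is a listed objective, and its analysis has its own entry in section 2.2. But this sentence goes beyond tense: it gives a comparative result as the reason for the next test.
- **Amount of repetition.** On the literal one-arm reading the conditional rate is only 9–14%, so the ANOVA would be mostly not a repeat of the t-tests. That stands, but on that reading it also fails to address the between-arm objective.
- **Tukey B.** No condition is attached to it, so the text does not show that it too was triggered by the t-tests.
- **Normality.** That statement shows results inside a plan. It is not evidence that the ANOVA was selected on outcomes.

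**Conclusion.** The concern holds in a limited form. The SAP states outcome results and makes the significant t-tests the reason for the repeated ANOVA, with no gate, significance level or rule for the other case. The topic was planned; as written, the decision to run this analysis was not independent of the data. It therefore cannot count as pre-specified or as independent confirmation of the t-tests.

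Given the trigger and no true effect, a between-arm effect follows in about 31–50% of trials and a lumbrokinase-only time effect in about 9–14%, against 5% ungated. These figures rest on the assumed test level, 20 to 22 patients per arm, three visits, normality and correlations of 0.3 to 0.7. The SAP defines neither the trigger nor the effect tested. The figures illustrate dependence and are not estimates of this trial's error rate. The t-tests themselves are not affected by this point.

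**What to change.** In section 2.2, specify a repeated-measures analysis of the symptom scores (DHI and VSS-SF) in both arms, with the arm-by-time comparison, and name the visits in the model. Run and report it whatever the t-tests show.

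If a dated plan from before unblinding exists, produce it and cite it. If not, keep the statement that the analysis followed the t-test results, label the analysis post hoc and exploratory, and rest no confirmatory claim on it. Simply deleting the clause would be a mistake: it is the only disclosure of the dependence, and without it a possibly post hoc analysis would look planned. Tukey B should carry the same label if it was run as a follow-up to this ANOVA.

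The cost is some wording in the SAP and report, a few extra model runs, and a weaker claim for the time-course result. No new data are needed.

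### The fifth objective is a between-arm difference in time to improvement, but no analysis in the SAP estimates or compares such a time, and improvement is never defined

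*Combined protocol and SAP*

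**What the plan says.** - **Objective (section 1.1).** The fifth of five objectives concerns the difference in "Time to improvement of dizziness symptoms between BPPV patients receiving oral lumbrokinase DLBS1033 therapy and those receiving betahistine therapy". None of the five is named as primary.
- **Variable (section 1.2).** The outcome appears in the variable list: "Dependent variables: inflammation level, quality of life, time to improvement of dizziness symptoms in BPPV patients". Under "Operational definition of research variables" only BPPV therapy is defined. No score threshold, event rule or starting point for the time is given anywhere.
- **Analysis (section 2.2).** The one item on symptom improvement time states that "further analysis regarding the time to symptom improvement in BPPV patients receiving oral lumbrokinase DLBS1033 was performed using multiple repeated ANOVA". It opens with the condition "Given the significant statistical differences found with the independent T-test". Betahistine patients are not mentioned in it.
- **Neighbouring items (section 2.2).** Independent t-tests compare the arms on mean DHI, mean VSS-SF and three biomarkers at days 7 and 14. The post-hoc line reads "Tukey B post-hoc test was used to compare the mean scores/levels between groups".
- **Timing (section 1.2).** Data collection "continued until the required sample size was met, from April to August 2024", so it is complete.

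**The concern.** A between-arm objective needs a between-arm analysis of the quantity it names. Here the quantity is a time. It has no definition, and the only analysis listed for it is an ANOVA described for one arm. A significant fall in scores among lumbrokinase patients could be reported as faster improvement even if betahistine patients improved equally fast or faster. The ANOVA is also conditional on t-test results, so whether it is run depends on the data. At stake is one conclusion out of five: that patients on one drug improve sooner.

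**Working it through.** The plan gives no figure for this item, so there is none to reproduce. The check sets the objective against each analysis in section 2.2 and then sizes what the data could support.

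**1. What each analysis compares**

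| Item in section 2.2 | Arms compared? | Quantity |
|---|---|---|
| t-tests, day 7 and day 14 | Yes | Mean score or level on a fixed day |
| Repeated ANOVA, read as one arm | No | Change in mean score within lumbrokinase |
| Repeated ANOVA, read as two arms | Yes | Mean scores across visits |
| Tukey B | Yes | Mean scores or levels |

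No row has both the arms compared and a time as the quantity.

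**2. What the one-arm reading can detect (illustration)**

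All inputs are assumed: 20 patients per arm, scores at days 0, 7 and 14, within-patient correlation 0.5, 4,000 simulated trials. The documents do not name a day 0 questionnaire score.

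- Arms identical, both falling 0.5 SD by day 7 and 1.0 SD by day 14: the lumbrokinase-only ANOVA is significant in 98% of trials and the arm-by-visit test in 5%.
- Betahistine faster, with its full 1.0 SD fall reached by day 7: the lumbrokinase-only ANOVA is again significant in 98%.

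The one-arm result is the same whichever arm improves sooner. This bears only on the one-arm reading.

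**3. How finely time could be known**

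The only assessment days named in section 2.2 are 7 and 14. If improvement is read only at those visits, its time has at most three classes: by day 7, day 8 to 14, not by day 14. On that condition, an arm in which everyone improved on day 1 and an arm in which everyone improved on day 6 would both show 100% by day 7. Because the variable is undefined, a day of improvement reported by the patient is not excluded; the three-class limit would then not apply.

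**4. Precision of a two-arm repair**

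Inputs from section 1.2: minimum sample 40, planned total 44. Equal arms are assumed, giving n = 20 or 22.

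Score difference at one visit, 95% half-width = t(0.975; 2n − 2) × √(2/n) SD:
- n = 20: 2.024 × 0.316 = 0.640 SD
- n = 22: 2.018 × 0.302 = 0.608 SD

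Difference in proportion improved, Newcombe 95% half-width, with **equal observed proportions in both arms** (assumed):

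| n per arm | Improved in each arm | Half-width |
|---|---|---|
| 20 | 4 or 16 | 0.247 |
| 20 | 6 or 14 | 0.268 |
| 20 | 10 | 0.284 |
| 22 | 4 or 18 | 0.231 |
| 22 | 7 or 15 | 0.260 |
| 22 | 11 | 0.273 |

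With unequal proportions the interval is asymmetric. For 16/20 against 8/20 the difference is 0.80 − 0.40 = 0.40, and the interval reaches about 30 points below it and 22 above. These figures describe the repair, not the size of the error in the plan.

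**The case against.** Four points can be made for the plan.

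- **The t-tests already compare the arms.** This stands. A lower mean VSS-SF at day 7 in one randomised arm is direct, if coarse, evidence of earlier benefit. A reader might infer from the gap that the plan can say nothing about which arm benefits earlier; the t-tests rule that out. They compare means on fixed days, however, and do not estimate a time.
- **The ANOVA may include both arms.** This is plausible, because the Tukey B line refers to groups. The absence of a stated arm-by-visit term proves little, since section 2.2 lists no model terms for any analysis. It would be wrong to infer that betahistine patients were certainly left out. But on the two-arm reading the analysis still compares scores rather than times, and improvement is still undefined.
- **The past tense shows nothing.** Agreed. Most of the document is in the past tense, so tense is no evidence that this step was chosen after results were seen. The point rests on content alone: the step is made to follow significant t-tests.
- **A two-arm score model does not estimate a time either.** True, which is why the fix pairs it with a definition of improvement or a restated objective.

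**Conclusion.** The concern holds in this form: no analysis in section 2.2 estimates or compares time to improvement between arms, and improvement has no definition. This is true on both readings of the ANOVA. It is an analysis that does not answer its objective, not only a lack of detail.

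The consequence is limited to one of five objectives. The randomised day 7 and day 14 comparisons of DHI and VSS-SF are unaffected by this point, and only a claim about time to improvement lacks support. It should be fixed before any such claim is made. The three-class limit assumes that improvement is read only at the two named visits. The precision figures assume equal arms and, for proportions, equal observed proportions of about 20% to 80%.

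**What to change.** 1. Replace the ANOVA item with a two-arm repeated-measures model of VSS-SF, and another of DHI, with arm, visit and arm-by-visit. Run both whatever the t-tests show. Report the arm difference with its 95% CI at day 7 and at day 14, and state that the model compares scores, not times. State whether a pre-treatment questionnaire score was collected, and adjust for it only if so.
2. Then choose one:
   - (a) State a definition of improvement and compare the proportion improved by day 7 and by day 14 between arms, with 95% CIs. Label both definition and analysis post hoc, because results may already have been seen. This answers the time question only coarsely.
   - (b) Restate the fifth objective as the difference in symptom score at day 7 and day 14, and disclose that the change came after data collection. This gives up the time question.
3. Make no claim of faster improvement from change within one arm. Label any retained one-arm ANOVA exploratory.

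The cost is wording plus a re-analysis of scores that the SAP already compares between arms, with no new patients or visits. The downside is a narrower or post hoc conclusion with wide intervals. The model in step 1 also yields four arm contrasts (two scores at two visits) with no primary among them, so they are best presented as estimates with intervals.
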